## Protocol

1. **Project Title:** The use of lavender aromatherapy to decrease women's anxiety and perception of pain during office hysteroscopy
2. **Investigators:**
  - a. Principal Investigator: [name], MPH
  - b. Co-Investigator: [name]
  - c. Co-Investigator: [name], MS
3. **Abstract:** Office hysteroscopy is an invaluable practice used to treat a myriad of gynecological processes in an outpatient setting. This is a minimally invasive procedure that aids in the diagnosis and treatment of uterine and cervical pathology such as endometrial polyps, malignancy, uterine septum, or submucosal myomas. Benefits of an outpatient procedure include decreased costs to the patient, avoidance of general anesthesia, and faster recovery times. However, a significant limiting factor is the perceived pain and anxiety associated with office hysteroscopy. Studies have shown that an increasing state of anxiety is often associated with high levels of pain perception and a high anxiety level can exacerbate pain. Lavender aromatherapy has been associated with decreased anxiety in a variety of clinical situations, including urodynamics and during hemodialysis. In a randomized study of healthy controls, treatment with lavender aromatherapy will significantly decrease the pain intensity associated with Office Hysteroscopy and stress/anxiety levels as measured on a visual analog scale when compared to control subjects receiving distilled water placebo. The purpose of this study is to determine a difference in patient-reported anxiety and pain levels before, during, and after office hysteroscopy in patients given lavender aromatherapy versus placebo. The goal of this study is to find methods to decrease anxiety and perceived pain to help facilitate more office hysteroscopy procedures as opposed to proceeding to the Operative Room.
4. **Background:** Office hysteroscopy is an invaluable practice used to treat a myriad of gynecological processes in an outpatient setting. This is a minimally invasive procedure that aids in the diagnosis and treatment of uterine and cervical pathology such as endometrial polyps, hyperplasia, malignancy, uterine synechia, uterine septum, or submucosal myomas. Benefits of an outpatient procedure include decreased costs to the patient, avoidance of general anesthesia, and faster recovery times. However, a significant limiting factor is the perceived pain and anxiety associated with office hysteroscopy. Many women experience anxiety around the procedure which can affect overall patient satisfaction. Studies have shown that an increasing state of anxiety is often associated with high levels of pain perception and a high anxiety level can exacerbate pain. Strategies that have been implemented to help reduce anxiety include

patient education, interaction during the procedure, communicating through traditional or multimedia approaches, and music listening.

Lavender aromatherapy has been associated with decreased anxiety in a variety of clinical situations, including urodynamics, percutaneous coronary intervention in an intensive care unit, preoperative patients, during facial cosmetic injections, pre-procedural for colonoscopy or esophagogastroduodenoscopy and during hemodialysis. Ozel and colleagues found that the use of lavender essential oil aromatherapy for urodynamic testing reduced anxiety in patients. There was a decrease in anxiety from baseline to catheter placement and 15 minutes post-procedure were greater in the lavender group compared to the control group. In this randomized study of healthy controls, treatment with lavender aromatherapy will significantly decrease the pain intensity associated with Office Hysteroscopy and stress/anxiety levels as measured on a visual analog scale when compared to control subjects receiving a distilled water placebo. The purpose of this study is to determine a difference in patient-reported anxiety and pain levels before, during, and after office hysteroscopy in patients given lavender aromatherapy versus placebo. Providing more opportunities for office hysteroscopy can decrease the need to perform the procedure in the Operating Room and reduce costs and patient exposure to Anesthesia. Managing anxiety and perception of pain can help improve patient experiences and increase the utility of office hysteroscopy.

5. **Specific Aims:** The purpose of this study is to determine a difference in patient-reported anxiety and pain levels before, during, and after office hysteroscopy in patients given lavender aromatherapy versus placebo.
6. **Research Plan:** This study design is a randomized placebo control pilot trial. Women scheduled for office hysteroscopy at the UF Shands Women's Health Clinic (Medical Plaza/Springhill) will be invited to participate. For this pilot study, we will approach 40 participants to account for 25% dropout rate and we will aim to enroll 30 participants with 15 participants in the lavender group and the placebo group, respectively. Participants who meet inclusion criteria will be randomized to the aromatherapy or the placebo group after informed consent is obtained (from PI or co-investigators) and before undergoing the hysteroscopy procedure. Randomization will occur via the sealed envelope system. Participants will be given a randomly generated treatment allocation concealed within an opaque envelope. Aside from randomization to aromatherapy versus placebo, no procedures will be performed for study purposes that would not be normally performed in the clinical evaluation. Prior to starting the procedure, the clinic nurse will prepare the aromatherapy versus distilled water on a paper towel by applying two drops of each solution on a paper towel. The patients will hold the paper towel over their nose and then they will be asked to take two deep breaths. Before the physician comes in, the nurse will ask the participant to take a deep breath while holding the towel 3 inches from her face and will instruct the participant to continue to take normal breaths subsequently. It will not be possible to blind the participants or the examiner to the assigned group since the lavender oil will have a different scent than the placebo. However, the use of distilled water on the towel will allow the possibility that the deep breathing accompanying the instruction may have an effect on

reported pain and anxiety. We will be using lavender (*Lavandula angustifolia*, Aura Cacia) essential oil and distilled water for the study and placebo arms, respectively. The oil is 100% pure essential oil obtained from steam distillation of fresh flowering tops and tested for purity by gas chromatography/mass spectrometry, specific gravity, optical rotation, and refractive index. The PI will incur a minor cost of \$13.29 associated with purchasing the lavender aromatherapy from Whole Foods Market.

Vaginoscopy approach will be utilized to perform the procedure. This avoids the use of a speculum in the vagina or tenaculum to grasp the cervix. This atraumatic technique reduces pain stimuli generated from the cervix and the vagina when using manipulating instruments. Vaginoscopy relies on hydrodilation of the cervical canal for entry of a miniaturized scope. This technique involves distending the vaginal vault with normal saline and advancing the scope to the posterior fornix. Gently pulling back until the external cervical os is visualized and then the scope is advanced into the cervical canal.

The participant will undergo the standard clinic exam in a standardized order. The participants will complete the Hospital Anxiety and Depression Survey (HADS) at baseline. The HADS is a reliable instrument for detecting states of depression and anxiety in the setting of a hospital medical outpatient clinic. This will be used to establish their baseline anxiety levels. Participants will then be asked to rate their level of anxiety and pain immediately before beginning the exam, immediately after catheter placement, and 15 min after termination of the study using a 10-point visual analog scale and the Wong-Baker pain scale. At the end, the participants will also be asked to rate their satisfaction with the visit overall on a visual analog scale. Our primary objective is to determine the change in anxiety scores on the visual analog scale from baseline to immediate post-procedure.

- Inclusion Criteria:
  - Women aged 18 and over
  - Scheduled to undergo office hysteroscopy procedure
  - Able to give informed consent
  - Able to read and write in English
  - Anxiety score > 0 on a numerical scale at baseline
- Exclusion Criteria:
  - Any contraindication to office hysteroscopy (active pelvic infection, confirmed cervical or endometrial cancer severe hypertension, or any other condition that might be worsened by an uncomfortable test)
  - Allergy to lavender oil, or any of its components
- Withdrawal Criteria
  - The patient requests terminating participation

Flow of Events:

- The Principal Investigator or Co-Investigator will approach patients who are scheduled to undergo Office Hysteroscopy at each clinical site. PI (Resident Physician) and Co-Investigator (Attending Physician).
- Participants who agree to participate will be enrolled in the study and PI/Co-Investigator will conduct informed consent with the participant.
- Prior to starting the hysteroscopy procedure, the participants will complete a baseline questionnaire and a Hospital Anxiety and Depression Survey (HADS).
- Participants will be randomized into two groups (aromatherapy or placebo).
- Participants will hold a paper towel over their nose and take two deep breaths.
- For each group, the protocol will be the same except the towel held over the nose will be scented with lavender oil or distilled water.
- The hysteroscopy procedure will proceed under a standardized protocol that is not directly related to the study.
- Participants will be asked to rate their level of anxiety and pain immediately before, after, and 15 minutes after completing the procedure. Participants will be monitored for 30 minutes post-procedure and participation in the study will conclude at the end of this time interval.

7. **Possible Discomforts and Risks:** The risks and discomforts with this study are based on baseline risk/discomforts associated with the hysteroscopy procedure. Specifically related to the study, the risk involves exposure to Lavender oil and possible side effects associated with this exposure. We do not anticipate any significant complications associated with the procedure or the study oil. However, we will monitor the participant for at least 30 minutes post-procedure for side effects related to the oil, such as nausea, vomiting, headache, or allergic reaction. Women are given verbal and written post-op instructions by the clinic nurse upon discharge. Participants will be provided with the phone number of the clinic and PI and will be instructed to contact the clinic and/or PI should have any questions or problems.

Additional risks include breach of confidentiality. To ensure the privacy of participant information, collected data will be stored on an electronic base encrypted database (Redcap) and this will only be accessible to study staff. Any additional research documents will be saved on a password-encrypted jump drive and locked in a filing cabinet in the Minimally Invasive Gynecologic Surgery office at the Springhill or Medical Plaza office. At the completion of the study, all personal identifiers will be destroyed in a HIPAA-compliant manner.

8. **Possible Benefits:** Participants may not receive any personal benefits from being in this study. However, others may benefit from the knowledge gained from this study. Information gathered from this study can help standardize hysteroscopy procedures by implementing potential stress relievers. The risks posed to participants are minor and very rare. The benefits of gaining more knowledge or how to adjust future patient care makes this study worthwhile. Participants

randomized to the aromatherapy treatment arm may benefit from perceived reduction in pain and anxiety associated with the hysteroscopy procedure.

9. **Conflict of Interest:** No conflict of interest associated with this study.

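### No clearly defined rating covers the 'during' part of the aim, and the protocol's two rating schedules disagree

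*Protocol*

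**What the plan says.** The title of the protocol is "The use of lavender aromatherapy to decrease women's anxiety and perception of pain during office hysteroscopy". The Abstract, the Background and Section 5 (Specific Aims) all give the purpose as to "determine a difference in patient-reported anxiety and pain levels before, during, and after office hysteroscopy".

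Section 6 (Research Plan) then gives two rating schedules:

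- The narrative asks for anxiety and pain ratings "immediately before beginning the exam, immediately after catheter placement, and 15 min after termination of the study".
- The Flow of Events asks for them "immediately before, after, and 15 minutes after completing the procedure".

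The narrative also fixes the primary objective: "Our primary objective is to determine the change in anxiety scores on the visual analog scale from baseline to immediate post-procedure". It describes the technique as vaginoscopy: "Vaginoscopy relies on hydrodilation of the cervical canal for entry of a miniaturized scope". No catheter step appears in that description. The Background does mention one, in its account of the urodynamics pilot: "There was a decrease in anxiety from baseline to catheter placement and 15 minutes post-procedure", with both decreases said to be greater under lavender than under control.

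**The concern.** The word 'during' stands in the title and in every statement of the purpose, so it is not a slip. Staff who work from the Flow of Events would nevertheless collect nothing labelled as a rating of the procedure. Staff who work from the narrative would look for a catheter placement that does not occur. They would have to guess at an equivalent moment or leave the rating out, and they would have no immediate post-procedure score for the primary objective.

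Both versions ask only for a level of anxiety and pain. They do not say whether the woman should report how she feels now, how she felt on average, or the worst she felt with the scope in place. One participant may answer for the present and the next for the procedure. With 15 per arm, such a mixture would cloud the comparison.

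A later analysis plan cannot repair this, because a question that was not asked at the visit, or was asked without a reference period, cannot be recovered from the data.

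**Working it through.** The protocol gives no figure on this point. Its one planning figure reproduces, 30 / (1 − 0.25) = 40 women approached for 30 enrolled, but plays no part here. The check is a comparison of time points.

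| Time of rating | Aim (Section 5) | Section 6, narrative | Section 6, Flow of Events | Primary objective |
|---|---|---|---|---|
| Before the procedure | wanted | yes | yes | needed, as baseline |
| During the procedure | wanted | only if catheter placement means scope insertion | no | not needed |
| Immediately after | wanted, as part of 'after' | no | yes | needed |
| 15 minutes after | wanted, as part of 'after' | yes | yes | not needed |

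Two readings are assumed. The narrative's last rating, timed from termination of the study, is taken to mean 15 minutes after the procedure, as in the Flow of Events. Baseline in the primary objective is taken to be the rating just before the procedure.

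1. **Flow of Events.** One rating before, none during, two after: 1 + 0 + 2 = 3. The primary objective is covered. The 'during' part of the aim is not.
2. **Narrative.** One rating before, one at catheter placement, one at 15 minutes: 1 + 1 + 1 = 3. The middle one lies within the procedure only if it is read as scope insertion. The immediate post-procedure rating is absent, so the primary objective is not covered.
3. **Both together.** The table has four distinct times. Each schedule lists three of them, and they share two (before, and 15 minutes after). Neither serves both the full aim and the primary objective.
4. **Origin of the catheter time.** The vaginoscopy paragraph has a scope entering the cervical canal by hydrodilation and no catheter. The only other mention of catheter placement is in the Background, for the urodynamics pilot. The phrase matches that study's time point and is not defined for this procedure.
5. **Reference period.** Neither schedule says 'now', 'worst' or 'on average'. The immediate post-procedure rating could therefore capture procedural pain and anxiety by recall, but the text does not ask for that.

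**The case against.** The best defence is that the during-procedure rating exists and is merely mislabelled: read catheter placement as scope insertion and the narrative supplies it. That reading is plausible, and it means one cannot say that the protocol as a whole contains no such rating. It does not settle the matter. The protocol never states the equivalence, the Flow of Events does not carry the rating, and the same narrative schedule still lacks the post-procedure score for the primary objective.

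A second defence is that a woman asked straight after the procedure may well report what she has just been through. That is possible too. What stands is that the reference period is left open.

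Three stronger conclusions are tempting, and the document supports none of them:

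- **A reader might infer that the trial cannot answer its title question.** The stated primary objective concerns the change in anxiety to immediately after the procedure, and the Flow of Events collects that rating. The gap is confined to the 'during' part of a broader aim.
- **A reader might infer that post-procedure ratings measure only relief and sit near the bottom of the scale, so that a real effect would be missed.** The protocol has no current-state wording and no score distribution. Its own account of the urodynamics pilot ("There was a decrease in anxiety from baseline to catheter placement and 15 minutes post-procedure") reports the larger lavender decrease at the later time as well as at catheter placement. That weighs against any claim that a rating after the procedure cannot show an effect.
- **A reader might try to quantify how much effect is lost by rating after the procedure.** The document gives no means or standard deviations at either time, so any such factor would rest wholly on assumed values.

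**Conclusion.** The point holds as a defect in how the outcome times are defined. The title and aim ask about anxiety and pain during hysteroscopy, and no clearly defined rating covers that period: 0 of 3 ratings in the Flow of Events, and 1 of 3 in the narrative at a moment that the described procedure does not contain. The two schedules also contradict each other on the middle rating, and only the Flow of Events supplies what the primary objective needs. The missing reference period adds ambiguity to every score taken after the procedure.

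The primary objective remains answerable if the Flow of Events is followed. The size of any loss for the 'during' outcomes cannot be estimated from the document. The conclusion rests on comparing the text alone and needs no assumption about score levels or effect sizes. It should be corrected before ratings are collected, but it does not undermine the trial as a whole.

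**What to change.** Reconcile the narrative and the Flow of Events in Section 6 into one schedule, stated once, as follows:

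1. Keep the rating before the procedure, the immediate post-procedure rating and the 15-minute rating. State that the last is timed from the end of the procedure.
2. Replace catheter placement with a defined moment of the hysteroscopy, or delete it.
3. At the immediate post-procedure rating, add two separately worded visual analog items: worst pain during the procedure and worst anxiety during the procedure. Name them as the secondary 'during' outcomes, so that the primary objective is unchanged.
4. Word the other ratings explicitly as current state.

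If the added items are not wanted and no during-procedure rating is defined, the word 'during' should come out of the aim.

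The cost is two more items at a rating already scheduled, with slightly more burden for participants. The recalled items have a real weakness. Section 6 states that participants cannot be blinded because of the scent, so their recall of the worst moment is open to expectation bias as well as ordinary recall error. The protocol should say so where it names these outcomes.

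### Section 6 gives two conflicting rating schedules, and only the one in the Flow of Events includes the immediate post-procedure rating that the primary objective needs

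*Protocol*

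**What the plan says.** Section 6 (Research Plan) of the protocol sets out the timing of the anxiety and pain ratings twice.

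- **Narrative on outcome measures:** ratings are taken "immediately before beginning the exam, immediately after catheter placement, and 15 min after termination of the study".
- **Flow of Events:** "Participants will be asked to rate their level of anxiety and pain immediately before, after, and 15 minutes after completing the procedure".

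The narrative paragraph also states the primary objective: "the change in anxiety scores on the visual analog scale from baseline to immediate post-procedure".

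Three other statements bear on how these are read.

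- The procedure is vaginoscopic hysteroscopy: "Vaginoscopy relies on hydrodilation of the cervical canal for entry of a miniaturized scope". No catheter is mentioned in its description.
- Section 5 (Specific Aims) refers to ratings before, during and after hysteroscopy.
- The Flow of Events has women monitored for 30 minutes after the procedure, and "participation in the study will conclude at the end of this time interval".

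**The concern.** The second rating is the one the primary objective depends on, and the two schedules disagree about it. The narrative ties it to an event that this procedure does not have. The nearest equivalent is entry of the scope, which would make it a rating during the procedure. The Flow of Events and the primary objective place it after the procedure.

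Anxiety while the scope is being placed and anxiety once it is out are different quantities. A self-rating not taken at the right moment cannot be reconstructed afterwards, and no later analysis plan can supply it. The trial aims for 30 women, 15 per group, at two clinic locations, so there is little room for lost or mistimed primary ratings.

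**Working it through.** No formula or stated figure is involved. The check matches each scheduled rating to the time point in the primary objective.

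| Rating | Narrative | Flow of Events | Needed for the primary objective |
|---|---|---|---|
| 1 | Just before the exam | Just before the procedure | Yes, taken here as the baseline |
| 2 | After catheter placement (no such step; scope entry at the nearest) | After the procedure | Yes, immediately post-procedure |
| 3 | 15 min after the end of the study | 15 min after the procedure | No |

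**Step 1: immediate post-procedure ratings.** The narrative has 0 of 3 and the Flow of Events has 1 of 3. The second count takes the word immediately to apply to the after-procedure rating as well as the before-procedure one, which is the natural reading.

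**Step 2: the catheter anchor.** Elsewhere in the protocol, catheter placement appears only in Section 4 (Background), in the summary of the cited urodynamics trial: "There was a decrease in anxiety from baseline to catheter placement and 15 minutes post-procedure were greater in the lavender group". Both time points named there, catheter placement and 15 minutes post-procedure, resemble ratings 2 and 3 of the narrative. That the wording was carried over is an inference. The finding does not need it, because the anchor is undefined for hysteroscopy whatever its origin.

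**Step 3: can staff resolve it themselves?** Two readings are open, and each has support in the text.

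- Catheter placement means scope insertion. This serves the during-procedure part of the aim but leaves the primary time point without a rating.
- Catheter placement means the end of the procedure. This serves the primary objective and agrees with the Flow of Events but leaves nothing for the during-procedure part of the aim.

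Taken together, the aim, the primary objective and the two schedules call for four times: before, during, immediately after and 15 minutes after. Each schedule has three.

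**Step 4: the third rating.** If the end of the study means the end of the examination, the rating falls 15 minutes after the procedure and the two schedules agree. If it means the end of participation, it falls at 30 + 15 = 45 minutes, after the woman has left the trial. The first reading is the more natural one, so this is a fault of wording only.

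**Step 5: scale.** One missed or mistimed primary rating is 1/15 = 6.7% of an arm. The protocol gives no basis for estimating how many would be affected or by how much the scores would shift.

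**The case against.** The strongest reply is that the Flow of Events already settles the matter. It belongs to Section 6, it schedules a rating after the procedure, and it matches the primary objective. The catheter anchor cannot be followed literally, so staff would fall back on the usable text. On this view there is a slip of wording and no loss of data.

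Much of that stands. A reader of the narrative alone might infer that the primary outcome is not collected at all. The protocol does not support that, because the Flow of Events does schedule the rating. A reader might also infer that the last rating falls after participation has ended. That rests on the literal reading in step 4; the sentence runs from the start of the exam to its termination, and 15 minutes agrees with the Flow of Events. Nor does anything in the protocol show that the two locations would work from different text, so a primary variable mixing two time points is a risk and not a certainty.

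The reply fails on one point. It assumes that staff will read the impossible anchor as the end of the procedure. Scope insertion is the closer analogue of placing a catheter, and the stated aim of measuring during the procedure supports it. A careful reader could therefore follow the narrative in good faith and not take the primary rating at its stated time.

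**Conclusion.** The concern holds as an internal contradiction. Section 6 contains two rating schedules that differ on the second rating, and only the Flow of Events supports the primary objective. The narrative schedule has no immediate post-procedure rating and depends on a step that the described procedure lacks.

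The consequence is conditional. If staff follow the narrative, or differ in which text they follow, some or all primary ratings may be missed or taken during insertion. The size of any resulting bias cannot be calculated from the protocol.

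The conclusion assumes that catheter placement has no unstated meaning in this clinic's hysteroscopy, and that the after-procedure rating in the Flow of Events is meant to be immediate. It should be corrected before enrolment because the affected rating is the primary one, its loss is irrecoverable and the correction is cheap.

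**What to change.** Reconcile the narrative and the Flow of Events into one schedule, stated identically in both places and tied to hysteroscopy events:

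1. immediately before the procedure;
2. immediately after the procedure ends, named as the primary time point;
3. 15 minutes after the procedure ends.

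Replace the catheter and end-of-study anchors with these.

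Then settle the during-procedure part of the aim. Either give that rating its own defined time point, separate from the primary one, or remove the word from the aim wherever it is stated.

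The cost is a wording amendment and a matching data-collection form, with no extra visits. Keeping the during-procedure rating adds one brief rating per woman.

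### The moment of the primary anxiety rating is not fixed: the two rating schedules disagree, and neither places the rating before findings are discussed or records whether they were

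*Protocol*

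**What the plan says.** The primary objective, in the text of section 6 (Research Plan), reads: "Our primary objective is to determine the change in anxiety scores on the visual analog scale from baseline to immediate post-procedure".

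The same section, shortly before, sets the anxiety and pain ratings at these times: "immediately before beginning the exam, immediately after catheter placement, and 15 min after termination of the study". The Flow of Events list, later in section 6, sets them differently: "Participants will be asked to rate their level of anxiety and pain immediately before, after, and 15 minutes after completing the procedure".

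The Background (section 4) describes office hysteroscopy as a procedure that "aids in the diagnosis and treatment of uterine and cervical pathology such as endometrial polyps, hyperplasia, malignancy" and other conditions; the Abstract (section 3) says much the same. The exclusion criteria remove women with "confirmed cervical or endometrial cancer severe hypertension" and other contraindications, so only cancer that is already confirmed keeps a woman out.

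On conduct, the Flow of Events says: "The hysteroscopy procedure will proceed under a standardized protocol that is not directly related to the study". On blinding, section 6 says: "It will not be possible to blind the participants or the examiner to the assigned group". No section says when a participant is told what was seen, and none provides a field to record it.

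**The concern.** The primary outcome is self-reported anxiety close to the end of a procedure that can be diagnostic. What a woman is told about her uterine cavity, reassuring or worrying, may change her anxiety for reasons unrelated to the scent. If some women complete the scale before that conversation and others after it, the score mixes two things. The analysis cannot separate them, because nobody has recorded which came first.

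The conflict between the schedules makes this worse. Depending on which text the clinic follows, the rating used for the primary outcome could fall during the examination, at its end, or 15 minutes later, and these moments are not equally exposed to news. In an open-label comparison with 15 women per arm, precision is at stake first. Protection against disclosure that differs by arm comes second.

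**Working it through.** **1. The texts side by side**

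| Source | First rating | Middle rating | Last rating |
|---|---|---|---|
| Primary objective (section 6) | Baseline | Immediate post-procedure | Not used |
| Schedule in the text of section 6 | Just before the exam | Just after catheter placement | 15 min after the end |
| Flow of Events (section 6) | Just before | After the procedure | 15 min after |

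Only the Flow of Events supplies the rating that the objective needs. The section 6 account of the procedure describes a scope and mentions no catheter. The Background gives catheter placement and 15 minutes post-procedure as time points of a urodynamics trial. On the section 6 schedule, the middle rating would come before the examination is complete, and the only rating after it would be the 15-minute one, where findings are at least as likely to have been discussed.

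**2. The plan's own numbers**

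The protocol gives no SD, effect size, alpha or power, so there is no power calculation to reproduce. The one calculable figure is the number approached: 30 / (1 − 0.25) = 40, which agrees with the text.

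**3. Noise if disclosure is unrelated to arm (all inputs assumed)**

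Let the SD of the anxiety change without news be 2.5 points, let a proportion p of women hear worrying news before rating, and let it raise their score by δ points. Then variance = 2.5² + p(1 − p)δ², and effective n = 30 × 6.25 / variance.

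- p = 0.1, δ = 2: variance 6.25 + 0.36 = 6.61; SD 2.57; effective n 28.4.
- p = 0.2, δ = 4: variance 6.25 + 2.56 = 8.81; SD 2.97; effective n 21.3.
- p = 0.3, δ = 4: variance 6.25 + 3.36 = 9.61; SD 3.10; effective n 19.5.

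The loss runs from 1 − 28.4/30 = 5% to 1 − 19.5/30 = 35% of the information. The expected bias in the lavender-placebo difference is zero throughout.

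**4. The same noise as power**

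Take SD 2 to 3, p = 0.05 to 0.20, δ = 2 to 4, 15 per arm, two-sided 5% and the normal approximation. The variance is multiplied by 1.02 to 1.64. For a difference that would otherwise have 80% power (2.56 points at SD 2.5), power becomes 79% at best and 59% at worst.

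**5. The same noise as chance imbalance**

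With binomial counts in two arms of 15, the probability that the arms differ by two or more women who heard worrying news is 19% at p = 0.05, 35% at p = 0.10 and 49% at p = 0.20. The resulting shift in the arm difference has SD δ√(2p(1 − p)/15): 0.16 points at p = 0.05, δ = 2, and 0.58 at p = 0.20, δ = 4. This is the noise of step 3 in another form, not an addition to it.

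**6. Bias if disclosure differs by arm**

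Bias = (difference in proportion told before rating) × δ. A gap of 10 to 30 percentage points with δ of 2 to 4 gives 0.1 × 2 = 0.2 up to 0.3 × 4 = 1.2 points. Nothing in the protocol indicates that such a gap exists.

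**The case against.** A reader might infer that the primary outcome measures the news rather than the lavender. The protocol does not support that. The outcome is compared between arms randomized by opaque envelope before the procedure, so news unrelated to arm affects both arms equally in expectation. The stronger reading would fit a single-arm before-and-after study.

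A reader might also infer that the examiner tells women the findings at the chairside, perhaps differently by arm. The protocol says only that the examiner cannot be blinded. It does not say when, where or by whom findings are given. The list of pathologies describes the uses of hysteroscopy in general, not the indications in this sample. The Flow of Events says that the groups are handled identically apart from the scent, which weighs against arm-dependent handling even though it does not mention disclosure.

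A rating called immediate leaves little time for a conversation, and every input to the size is assumed. At the low end the loss is under two women in 30. The trial is also a pilot with no stated power target, and the order of a form and a conversation could sit in a data-collection procedure.

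Most of this stands, and it limits the claim. It does not remove the gap. A time called immediate does not order the form relative to a remark made as the scope comes out, and the section 6 schedule does not contain that time at all. A statistical analysis plan can neither order a bedside rating nor recover a status that nobody recorded.

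**Conclusion.** The concern holds in a limited form. The protocol fixes the time of its primary measurement badly: the objective and one schedule imply a rating that the other schedule omits, and neither controls or records whether findings were discussed first. News of findings could enter the score as well as any effect of lavender.

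If disclosure is unrelated to arm, the cost is precision. With an SD of change of 2.5 it ranges from about 5% to about 35% of the information in 30 women. That range rests entirely on the assumed frequency and effect of worrying news, so no particular size is established. Systematic bias, 0.2 to 1.2 points on the assumed inputs, would need disclosure to differ by arm. That is possible with an unblinded examiner but not shown. This is a correctable weakness in the measurement procedure and does not invalidate the primary outcome. It should be corrected before enrolment because it cannot be repaired afterwards.

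**What to change.** - Reconcile the schedule in the text of section 6 with the Flow of Events, so that both list the same ratings and both include the immediate post-procedure rating named in the objective. Either define the catheter-placement rating for this procedure or remove it.
- Define the immediate post-procedure rating as completed once the scope is withdrawn and before any findings are discussed.
- At this rating and at the 15-minute rating, record whether findings had already been discussed (yes/no) and, if yes, whether they were reassuring or concerning. Report both fields by arm.

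If the investigators prefer not to sequence the conversation, the recorded fields alone would still make any imbalance visible.

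The cost is a few sentences, two form fields and a short delay, about a minute, while the scale is completed. The content of counselling does not change.
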